covered by their insurance or patient assistance programs arranged by the study team. Patients will be asked to see their neurologist at least every 3 months to match the frequency of visits in the intervention arm and may see their PCP at their typical frequency. In the intervention arm, palliative care visits will be performed in person (or telemedicine if needed for rural areas and/or limited transportation or health issues) every 3 months. In addition, visits will be supplemented by phone calls one week after each visit to confirm understanding of team recommendations and at 6 weeks to check-in with patient and caregiver. Patients and caregivers may also contact the team as needed. Summaries of visits will be sent to the patient, caregiver, PCP and neurologist and suggestions for care outside of palliative care issues will be left to the patients' Usual Care team.

1.b. Sources of Materials

Data will be obtained from subjects non-invasively via interviews, questionnaires, cognitive testing, and neurological examination as described above.

This data will be accessible only to the research team and, if requested, by appropriate regulatory bodies such as the IRB and FDA. All documents generated by this study, including consent, will be stored in a locked filing cabinet in the locked office of the Principal Investigator (PI). Electronic data will be de-identified with the exception of a correlational spreadsheet including demographic information and study IDs for scheduling and safety contact purposes. This, and all other data, will be stored on a password protected network drive and backed-up on the hard-drive of the PI, also password protected, and kept in the PI's locked office. Identifying information will not be shared outside of the research team or regulatory bodies (e.g. IRB).

1.c. Potential Risks

There are minimal risks involved in the proposed research. There are no known significant risks from the intervention, interviews or surveys proposed for this study. Experiences from collaborators on this study suggest that most patients and caregivers welcome the opportunity to talk about their experiences, even on these potentially delicate subjects. Our interviewers will be cognizant of signs of emotional distress in participants and will suggest breaks and remind them that participation is voluntary. Cognitive testing and surveys as proposed in this study may induce boredom or restlessness. Any new diagnoses detected during screening (e.g. depression or dementia) will be referred for appropriate treatment, including emergent treatment if indicated. There are no known significant risks to the proposed team-based intervention for addressing palliative care needs. Participants will be reminded of the voluntary nature of this research and informed that we can follow them outside of the intervention or they can completely discontinue the study if they find it excessively burdensome or otherwise troubling.

2. Adequacy of Protection Against Risks

2.a. Recruitment and Informed Consent

Participants will be recruited from the academic medical centers (University of Colorado, University of California San Francisco, University of Alberta), associated clinics, community neurologists, and direct advertisements and contact with patients (e.g. clinicaltrials.gov, community seminars). Protocols will be approved by the relevant regulatory body at each institution before any contact is made with potential participants. We will obtain informed consent before any study related activities are performed. Potential subjects will be specifically told that their participation or lack of participation will not affect the clinical care they receive. For PD Dementia subjects, special procedures will be in place to involve both guardians and patients in the informed consent process, and both guardians and subjects will be required to give consent in person or by phone if performing visit by telehealth (or assent for PDD subjects unable to give full informed consent). The consenting process will use standard IRB terminology and will include a full description of expected subject involvement, procedures, risks, rights, and benefits. Capacity will be formally assessed in any patients with cognitive impairments and guardian consent and patient assent will be required in these cases.⁸³

2.b. Protections Against Risks

All subjects will be reminded that they can take breaks or discontinue the study at any time if they find it upsetting. PD dementia subjects will be required to give consent (if they have capacity) or assent with caregiver consent to avoid potential manipulation of a vulnerable population. Regarding patient privacy, all research procedures will be performed in a confidential setting. All documents generated by this study, including consent, will be stored in a locked filing cabinet in the locked office of the PI. Electronic data will be de-identified with the exception of a correlational spreadsheet including demographic information and study IDs for scheduling and safety contact purposes. This, and all other data, will be stored on a password protected

network drive and backed-up on the hard-drive of the PI, also password protected, and kept in the PI's locked office. Identifying information will not be shared outside of the research team or regulatory bodies (e.g. IRB).

3. Potential Benefits of the Proposed Research to Human Subjects and Others

All subjects participating will receive a free neurological examination and history from a movement disorder trained specialist, and screening for dementia and depression. These results will be reviewed by a study neurologist and referred for appropriate care if abnormalities are identified. Participants randomized to the usual care arm will have care with a neurologist arranged if they do not already have this in place. Participants randomized to the palliative intervention will have access and care from an interdisciplinary team. This proposal has the potential to further our knowledge of care models in PD and has the potential to influence our ability to address many currently unmet needs for patients and caregivers. As discussed below, the knowledge gained by this proposal has a significant potential to advance our knowledge of palliative needs in PD which has large positive implications for PD patients, the scientific community and society.

4. Importance of Knowledge to be Gained

Parkinson's disease (PD) affects 1-2% of adults over age 65 representing approximately 1.5 million Americans. Although PD is traditionally characterized by motor symptoms such as tremor and slowed movement more recent research shows that PD patients also commonly experience non-motor symptoms such as pain, fatigue, depression and dementia. PD interferes with patients' quality of life, leads to disability, decreases length of life and causes significant distress for caregivers. Unfortunately, many of the needs most important to patients and their caregivers (e.g. depression, planning for the future) are poorly addressed under current models of care. The goal of this proposal is to take a patient-centered approach to answering these questions. Our specific objectives are to: 1) Determine whether an outpatient palliative care team improves patient quality of life and caregiver distress compared to usual care with a neurologist; 2) Determine what patient and caregiver characteristics best predict benefit from palliative care services; and 3) Interview patients and caregivers to optimize service delivery and selection. This project is important to patients and their family caregivers because it assesses a new approach to PD care that has the potential to improve quality of life, caregiver burden and other important outcomes (e.g. nursing home placement). By testing the effectiveness of this approach and determining who benefits most we hope to provide a new option to assist those PD patients at highest risk for poor outcomes. Information generated by this proposal will also be important for other stakeholders interested in PD including hospitals, insurers and patient advocacy organizations.

5. Data and Safety Monitoring Plan

We will not assemble a Data and Safety Monitoring Board (DSMB) as this is a minimal risk study comparing the effectiveness of two currently available approaches to the care of PD and APD patients. The site PI will be notified of any adverse events occurring at all sites and will notify the study's central IRB (COMIRB) of all adverse events and any change in our appraisal of the risks and benefits of this study from our data or other published literature.

6. ClinicalTrials.gov Requirements

We will register this trial with clinicaltrials.gov prior to enrollment of the first participant at any site.

BIBLIOGRAPHY AND REFERENCES CITED

Citations

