Secondary Outcome Measures: Table 2 summarizes outcomes and other relevant data collected from patients and caregivers. To assess patient functional status and provide an alternate QOL measure we will administer the PDQ-39, the most commonly used measure of health-related QOL in PD. It was developed in 1995 on the basis of in-depth interviews of PD patients and has excellent psychometric properties and construct validity.^{40, 62} The PDQ-39 also provides validated subscores regarding mobility, activities of daily living, emotional well-being, stigma, social support, cognition, communication and pain. The PDQ-39 is sensitive to change over time with disease progression and improvement with interventions and minimally clinically important differences have been reported for the overall scale and subscores.⁶³ To assess symptom burden we will administer the ESAS-PD, a modified version of the Edmonton Symptom Assessment Scale.¹² The ESAS-PD was developed by [name] to incorporate common PD symptoms not in the original scale (e.g. confusion) and demonstrates adequate psychometric properties, including proxy reporting and sensitivity to change.¹² Other patient related outcomes will include: the Hospital Anxiety and Depression Scale (HADS)⁶⁴, the Prolonged Grief Questionnaire (PG-12; anticipatory grief)⁶⁵, and the Functional Assessment of Chronic Illness Therapy-Spiritual Wellbeing (FACIT-SW)⁶⁶ Other caregiver outcomes will include the HADS. Total time for all assessments is estimated to be 60-90 minutes and may actually be faster for more impaired patients due to reliance on proxy responses.

Table 2. Data Collected from Patients and Caregivers for Aim 1

Measure	Domain of Interest
Quality of Life: Alzheimer's Disease (QOL-AD) ³⁹	Patient Quality of Life (QOL)
Zarit Burden Interview (ZBI) ³⁴	Caregiver Distress
Parkinson Disease Questionnaire (PDQ-39) ³⁰	Patient Functional Status and secondary QOL
Edmonton Symptom Assessment Scale (ESAS-PD) ¹²	Patient symptom burden
Hospital Anxiety and Depression Scale (HADS) ³⁷	Patient and Caregiver Mood
Functional Assessment of Chronic Illness Therapy-	Patient and Caregiver Spiritual Wellbeing

Spiritual Wellbeing (FACIT-SP) ³⁹	
Patient Reported Outcome Measurement Information System (PROMIS-29)	Patient QOL (Validation of NIH Common Data Element)
Clinical Global Impression of Change	Patient, Caregiver and Clinician's global impressions of change
Prolonged Grief Questionnaire (PG-12) ⁴⁰	Patient and Caregiver Grief

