Unified Parkinson Disease Rating Scale ⁴¹	Patient Motor symptom Severity (motor exam only)
Montreal Cognitive Assessment (MOCA) ^{46, 56}	Patient Cognitive Status
Hoehn and Yahr Scale ⁴⁴	Patient Disease Stage (baseline visit only)
Charlson Comorbidity Index ^{61, 66}	Medical Comorbidities (baseline visit only)

Statistical Analysis: The main objective of the study is to determine the comparative effectiveness of interdisciplinary outpatient palliative care versus usual care with a neurologist for PD regarding effects on patient QOL and caregiver burden. The primary outcome variables will be the QOL-AD and the ZBI.^{40, 55} Secondary outcomes (see **Table 2**) include scales for symptom burden, mood, and spiritual wellbeing. Controlling covariates will include gender, age, disease severity (measured continuously using the Unified Parkinson Disease Rating Scale⁶⁷), cognitive dysfunction (measured continuously using the Montreal Cognitive Assessment⁶⁸), and baseline depression (measured continuously using the HADS Depression Subscale⁶⁴). The explanatory variables will be checked for randomization and multicollinearity. Successful randomization should minimize covariate imbalances between groups, but including them in the model can adjust for lingering confounding effects and account for variance in the outcome variable.

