The outcomes will be modeled with mixed regression model analysis, with correlation for repeated measures, at baseline and at 3, 6, 9, and 12 months. The empirical covariance estimator may be used to safeguard against model misspecification. The models will control for time, interaction between treatment and time, and potential baseline confounders, including gender, age, depression, and disease severity. The default model will have linear time trajectories for each treatment group, and linear functions for baseline controlling covariates. The linearity assumptions will be checked. Non-linear functions could be approximated with piecewise linear functions or transforms. The main contrasts will be the difference in areas under the fixed effect change from baseline curves for the palliative and treatment control groups, and the mean difference in change between 6 months and baseline between the groups. Secondary tests will be conducted for the mean difference in change from baseline between the groups at the 3, 9, and 12-month time points. The contrasts, controlled for all covariates, will be tested for significance using T-tests and F-tests, with an alpha level of 0.05. The effect estimates, 95% confidence intervals, and p values will be reported. In the process, the interaction between time and treatment will be tested. If the time trajectories are linear, then all tests are stochastically equivalent to the time by treatment interaction test with one parameter. Binary outcomes and count outcomes will be analyzed with logistic regression and Poisson regression respectively. Generalized mixed models will account for repeated measures. We plan to perform subgroup analyses for patients with dementia, severe disease, and depression and may perform exploratory subgroup analyses depending on primary results.

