Participants: Participants for Aim 3a will be identical to Aim 1. For Aim 3b (qualitative interviews), we will select a subgroup of participants and caregivers using purposive sampling to complete an additional interview following the final study visit to assess patient/caregiver satisfaction and suggestions of optimization of services and delivery. We will initially use a convenience sample, however as the study progresses we will use maximum variance sampling to ensure heterogeneity in terms of study site, gender, age, PD severity, and cognitive status. We may also use contextual information brought up in interviews or through Aim 3A to inform recruitment. We will interview patients assigned to both the intervention and usual care group as patients in the usual care arm may have less biases related to our service model or personal interactions with our team.

Primary Outcomes: Our primary outcome variables will be change at 6 months in the QOL-AD and ZBI. We will also look at symptom burden, mood, grief and spiritual wellbeing in secondary models.

Predictor Variables: Patient features will include: age, gender, medical comorbidities, presence of a caregiver, depression and disease severity (Hoehn and Yahr score). Caregiver features will include age, gender, depression, and socioeconomic status. Other variables including educational attainment, living situation (independent, assisted living, nursing home), location (rural, suburban, urban) and race/ethnicity will also be examined if sufficient variability in data permits.

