Statistical Analyses Aim 3a: Starting from the models in Aim 1, the effect modifiers will be introduced as interaction terms, so the time function for each treatment of group can be different for different levels of the interacting variable. The model with the interaction will be tested against the no interaction model. Interaction effects at individual time points may also be tested. The treatment effects for different levels of the interacting variable will be reported. For categorical interacting variables, the treatment effect will be reported at all levels of the interacting variable. For continuous interacting variables, the treatment effect will be reported at pre-specified values of the interacting variable (e.g. dementia and mild cognitive impairment cut-points for the Montreal Cognitive Assessment⁵⁴), natural boundaries (e.g. decades for age), or quartiles (e.g. for baseline caregiver burden). Categories will be collapsed when necessary and justified to prevent sparsely populated cells. An overall test for treatment effect across the different levels of the interacting variable will be performed as a multiple comparisons safe guard. Each interaction effects will be considered in separate models.

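### If patient HADS-Depression is the mood outcome, its baseline is both covariate and time-0 response, and on the listed terms its model-based standard error is about 20% too small

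*Combined protocol and SAP*

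**What the plan says.** All references are to the combined protocol and SAP.

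- **Covariates** (Aim 1, Statistical Analysis): gender, age, UPDRS, Montreal Cognitive Assessment and baseline depression, the last "measured continuously using the HADS Depression Subscale". No outcome is exempted from this set.
- **Mood as an outcome** (same section): the secondary outcomes "include scales for symptom burden, mood, and spiritual wellbeing". Under Secondary Outcome Measures the patient instrument is "the Hospital Anxiety and Depression Scale (HADS"), without saying whether the depression, anxiety or total score is meant. For caregivers, "Other caregiver outcomes will include the HADS".
- **Response vector** (Aim 1, Statistical Analysis): outcomes enter a mixed model "with correlation for repeated measures, at baseline and at 3, 6, 9, and 12 months", so time 0 is a response.
- **Model terms** (same section): time, treatment by time, and baseline confounders including depression. No treatment main effect is listed. The default is a linear trajectory for each arm. The empirical covariance estimator is offered as an option.
- **Power** (Aim 1, Sample Size and Power Considerations): the longitudinal calculations assume compound symmetry with correlation 0.5. The piecewise version has a common intercept for the two arms.
- **Aim 3a**: modifiers are added to the Aim 1 models. One reporting example for a continuous modifier is "quartiles (e.g. for baseline caregiver burden"). The ZBI is a primary outcome there, and for mood and others the plan says "We will also look at symptom burden, mood, grief and spiritual wellbeing in secondary models". Depression is among the listed patient and caregiver predictors.

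**The concern.** A baseline score can be adjusted for in two standard ways: keep it as the first response, or take it out of the response vector and use it as a covariate. For patient HADS-Depression the plan, as written, does both. At time 0 the covariate then predicts the response far better than at later visits. A model that assumes equal variances and equal correlations averages over this and misjudges how much the baseline tells it about follow-up. At stake are the confidence interval and p value of one named secondary outcome. In Aim 3a the same overlap could affect any modifier that is the outcome's own baseline.

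**Working it through.** **Inputs.** From the plan: visits at 0, 3, 6, 9 and 12 months; correlation ρ = 0.5 with compound symmetry; 125 per arm; alpha 0.05. Assumed here: two-sided testing, unit SD, normal data, no treatment effect, and the plan's ρ applied to HADS.

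**1. Which model does the plan's own power figure imply?** The plan states 64 per arm for 0.5 SD at 6 months with 90% power.
- Common intercept: variance 1 − ρ² = 0.75, so n = 2 × 0.75 × (1.960 + 1.282)² / 0.5² = 63.0, rounded up to 64. This matches.
- Plain change score: variance 2(1 − ρ) = 1, which gives 85. This does not match.
- The common-intercept model also gives 0.355 SD at 125 per arm (stated 36%) and 0.418 SD at 90 per arm (stated 42%).

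The plan gives no standard error for HADS, so this step only identifies the model.

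**2. Put the baseline on both sides.** Let Y0 to Y4 be the five HADS-Depression scores, with Y0 also a covariate with a single slope b.
- Large-sample slope: b = (1 + 4 × 0.5)/5 = 0.6.
- Residual variance at time 0: (1 − 0.6)² = 0.16. At each later visit: 1 + 0.36 − 0.60 = 0.76.
- Residual covariance of time 0 with a later visit: 0.4 × (0.5 − 0.6) = −0.04. Between later visits: 0.5 − 0.6 + 0.36 = 0.26.
- Compound symmetry averages these. Variance = (0.16 + 4 × 0.76)/5 = 0.64. Covariance = (4 × (−0.04) + 6 × 0.26)/10 = 0.14. The fitted correlation is 0.14/0.64 = 0.22.

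**3. Linear time, common intercept (the listed terms).** Code time as t = 0, 0.25, 0.5, 0.75, 1, so Σt² = 1.875 and (Σt)² = 6.25.
- Model-based: information = (1/0.5) × [1.875 − (0.14/1.20) × 6.25] = 2.2917, variance 0.4364, SE = √(2 × 0.4364/125) = 0.0836 for the 12-month difference.
- True: the estimator puts weights −0.800, −0.036, 0.182, 0.400 and 0.618 on Y0 to Y4. Its variance is 0.5 × (Σw)² + 0.5 × Σw² = 0.5 × 0.1322 + 0.5 × 1.2165 = 0.6744, so SE = √(2 × 0.6744/125) = 0.1039.
- Ratio 0.0836/0.1039 = 0.804, so about 20% too small. At 6 months both halve, to 0.0418 and 0.0520.
- Implied type I error: 2 × [1 − Φ(1.96 × 0.804)] = 11.5%. Simulation gives 11.7% and 11.9% in separate runs.

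**4. Time as knots or categories, common intercept.**
- 6-month contrast: model variance 0.64 − 0.14²/0.64 = 0.609. The estimator is Y2 − 0.6875 × Y0, with true variance 1 + 0.473 − 0.6875 = 0.785. Ratio √(0.609/0.785) = 0.88, so 12% too small; simulated type I error 8.3%.
- Area contrast (weights 3, 3, 3, 1.5): model variance 26.68, true 46.06. Ratio 0.76, so 24% too small; simulated type I error 13.5%.

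**5. Range.**

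| Change in assumption | Linear | 6-month, knots | Area, knots |
|---|---|---|---|
| ρ from 0.3 to 0.8 | 17–22% | 9–15% | 21–27% |
| One-sixth dropout by month 6 | 22% | 14% | 26% |

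Under linear time, if the outcome is HADS total, the shortfall is 14–18%. If it is HADS anxiety, it is 3–8%. Both assume a depression–anxiety correlation of 0.5–0.7, which the plan does not give.

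**6. What removes it.**
- Drop the duplicate: variance 1/[2 × (1.875 − 6.25/6)] = 0.60, SE = √(1.2/125) = 0.098, or 0.049 at 6 months. Model and true SE agree; simulated type I error is 4.8–5.7%.
- Add a treatment main effect: the slope becomes purely within-person. Fitted within-person variance 0.64 − 0.14 = 0.5 equals the true 1 − ρ = 0.5, so the ratio is 1. SE = √(2 × (0.5/0.625)/125) = 0.113, or 0.057 at 6 months.
- Keep the duplicate but use the empirical estimator: ratio about 1.00, simulated type I error 4.9–5.4%.
- Remove time 0 from the response and keep baseline as covariate: simulated type I error 5.7%.

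**7. Aim 3a, modifier equal to the outcome's own baseline.** The simulated type I error of the three-way term is about 10–12% when the treatment and treatment-by-modifier intercept terms are left out, about 3–4% when they are included, and 5.2% with post-baseline responses only.

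**The case against.** The strongest reply is that the duplicate alone does not shrink the standard error; the arm intercept must also be missing. A separate linear trajectory per arm can be read as including its own intercept, and the explicit common intercept appears only in a power calculation for a piecewise model. With a main effect the model is calibrated. The plan also names the empirical estimator as protection against a misspecified model, and that works too. Both replies stand as far as they go. But the listed terms contain no main effect, the plan's 64 per arm needs the common intercept, and the estimator is optional. Validity therefore rests on a choice the plan has not made.

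The scope is also narrow. Exact duplication needs patient HADS-Depression, and the score is not named. Caregiver mood uses the caregiver's own HADS, while the covariate appears to be the patient's. Baseline burden is only a reporting example in Aim 3a and is absent from the Predictor Variables list, although the Specific Aims predict that caregiver burden will matter.

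Three stronger readings are tempting, and the documents do not support them:
- **All error bars are 20% too small.** The covariate is in every model, but the main QOL-AD and ZBI analyses do not have the same value on both sides.
- **Aim 3a intervals are uniformly too narrow.** The direction depends on lower-order terms that the plan does not spell out.
- **The likelihood has no maximum under an unstructured covariance.** The plan specifies no such structure.

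**Conclusion.** The point holds in a limited form, and its severity is minor. As written, a patient HADS-Depression model would carry its time-0 value as both covariate and response. On the listed terms, with linear time, compound symmetry at 0.5 and model-based standard errors, the treatment contrast's standard error is about 20% too small and the type I error about 12%. With knots the shortfall is 12% for the 6-month contrast and 24% for the area contrast. It is essentially zero with a treatment main effect or the empirical estimator. The result rests on the plan's power-section correlation being apt for HADS and on the depression score being the mood outcome. In Aim 3a an own-baseline modifier gives a miscalibrated test, in a direction that cannot be stated from the plan.

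**What to change.** Add to Aim 1, Statistical Analysis:
- Name the HADS score or scores that constitute the mood outcome.
- State that when the outcome is patient HADS (depression or total), baseline HADS-Depression is dropped as a covariate because the time-0 response already carries it. Alternatively, time 0 leaves the response and baseline stays as a covariate.

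Add to Statistical Analyses Aim 3a: when a modifier is the outcome's own baseline, such as baseline burden for the ZBI, use post-baseline responses only.

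Dropping the duplicate is preferable to relying on the other two remedies. At 6 months under linear time its true standard error is 0.049, against 0.052 with the duplicate and the empirical estimator and 0.057 with an added main effect.

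The cost is two or three sentences and slightly different code for the HADS model. Data collection, sample size and the main QOL-AD and ZBI analyses do not change.

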For a longitudinal model with non-linear time trajectories, the difference in area under the change from baseline curve can summarize treatment effect across all times. If the true time trajectory is linear, and we model it as a piece-wise linear function, with a common intercept and knots at each time point, and the outcome is difference in area under the change from baseline curve, then a sample size of 25 per treatment group (50 total) would achieve 90% power with an alpha level of 0.05 and an effect size equivalent to 50% of the standard deviation at 6 months (6 sd*months of area, 0.5 sd on average). A sample size of 125 per treatment group (250 total) would be virtual certain to detect the effect, even for very small alpha levels, and so a Bonferroni correction could be applied to handle multiple comparisons. A sample size of 125 per treatment group (250 total) would achieve more than 90% power with an alpha level of 0.05 and an effect size equivalent to 22.5% of the standard deviation at 6 months (2.7 sd*months area, 0.225 sd on average). For a test of mean difference in change from baseline at 6 months, a sample size 64 per treatment group (128 total) would achieve 90% power with an alpha level of 0.05 and an effect size equal to 50% of the standard deviation. A sample size of 125 per group (250 total) would almost certainly detect the effect. The test would have more than 90% power even after a Bonferroni adjustment for almost 50 tests. Alternatively, 125 samples per group (250 total) could detect an effect equal to 36% of the standard deviation with 90% power and an alpha level of 0.05. Alternatively, for our minimal dyad size of 90 samples per group (180 total) we could detect an effect equal to 42% of the standard deviation with 90% power and an alpha level of 0.05. All sample size calculations for longitudinal data models assume a compound symmetric covariance structure and a correlation of 0.5 for repeated measures on a participant which is relatively conservative for QOL measures.⁶⁹

Aim 2: Describe the effects of an interdisciplinary outpatient palliative care intervention on patient and caregiver costs and service utilization.

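### Aim 1 baseline covariates enter only as constant level shifts, so contrasts in change from baseline are only partly adjusted for covariates that predict rate of change

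*Combined protocol and SAP*

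**What the plan says.** All references are to the combined protocol and SAP.

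- **Aim 1, Statistical Analysis, covariates.** Five are named: gender, age, motor severity (UPDRS), cognition (MoCA) and baseline depression (HADS depression subscale). The reason given is that "including them in the model can adjust for lingering confounding effects and account for variance in the outcome variable".
- **Same section, responses.** Outcomes are modelled "with correlation for repeated measures, at baseline and at 3, 6, 9, and 12 months", so the baseline score is one of the repeated responses.
- **Same section, model terms.** "The models will control for time, interaction between treatment and time, and potential baseline confounders, including gender, age, depression, and disease severity". Neither a treatment main effect nor a covariate-by-time term is listed. The functional form is: "The default model will have linear time trajectories for each treatment group, and linear functions for baseline controlling covariates".
- **Same section, contrasts.** One main contrast is the between-arm difference in area under the change-from-baseline curve (AUC). The other is "the mean difference in change between 6 months and baseline between the groups". The plan adds: "The contrasts, controlled for all covariates, will be tested for significance".
- **Aim 1, Sample Size and Power Considerations.** The longitudinal model is described "with a common intercept and knots at each time point", under compound symmetry with correlation 0.5.
- **Aim 3, Statistical Analyses Aim 3a.** Only here do baseline variables interact with the time functions, and there as modifiers of the treatment effect.

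**The concern.** A main-effect covariate says that a patient with worse severity, cognition or mood sits higher or lower by the same amount at every visit. It cannot say that such a patient declines faster. Both main contrasts concern change, so the imbalance that matters most is imbalance in predictors of change, and the model has no term for it.

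That such predictors exist is plausible from the plan itself. The Significance section says the atypical disorders tend to progress faster and may form a third of the sample. Diagnosis is neither a stratification factor nor a listed covariate, so this supports only the general point that rates of change will vary between patients.

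At stake are a conditional error in the estimate when such a covariate is out of balance, some lost precision, and a report that claims fuller adjustment than the model delivers.

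**Working it through.** **1. Which intercept the plan uses.** Inputs from the Aim 1 power section: five visits, compound symmetry, ρ = 0.5, 90% power, α = 0.05 (two-sided assumed). (1.960 + 1.2816)² = 10.507, with square root 3.2415.

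Per-patient variances in the piecewise model:
- Common intercept: 1 − ρ² = 0.75 for 6-month change; 42.1875 for the AUC (visit weights 3, 3, 3, 1.5).
- Separate arm intercepts: 2(1 − ρ) = 1.0 and 69.75.

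| Figure | Plan | Common intercept | Separate intercepts |
|---|---|---|---|
| n per arm, 0.5 SD at 6 months | 64 | 2 × 10.507 × 0.75/0.25 = 63.04 | 84.06 |
| n per arm, AUC of 6 sd*months | 25 | 2 × 10.507 × 42.1875/36 = 24.63 | 40.7 |
| Detectable at 6 months, 125 per arm | 36% | 0.355 | 0.410 |
| Detectable AUC, 125 per arm | 2.7 | 2.66 | 3.42 |
| Detectable at 6 months, 90 per arm | 42% | 0.418 | 0.483 |

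The linear-slope figures in the Aim 3 power section agree. Measure time in units of 6 months: t = 0, 0.5, 1, 1.5, 2, with Σt = 5 and Σt² = 7.5. Let k = ρ/(1 + 4ρ) = 1/6. The per-patient variance of the 6-month effect is (1 − ρ)/(7.5 − 25k) = 0.5/3.333 = 0.15. With 63 per cell:
- Within a subgroup: 3.2415 × √(2 × 0.15/63) = 0.224 (plan 23%; separate intercepts 0.258).
- Difference in effects: 3.2415 × √(4 × 0.15/63) = 0.316 (plan 32%; separate intercepts 0.365).

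The plan's figures therefore rest on a common intercept.

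**2. What main-effect adjustment achieves under that model.** Because the arms share a baseline mean, a constant between-arm shift does not vanish from the estimated 6-month effect. It passes through at 1 − ρ = 0.50 in the piecewise model. In the linear model it passes through at (5 − 25k)/(7.5 − 25k) = 0.833/3.333 = 0.25. Adjustment removes that part and lowers the between-patient variance. If the covariates explain an assumed share R² of 0.1 to 0.4 as a pure level effect, the adjusted/unadjusted SE ratios are:
- 6 months, piecewise: 0.981 to 0.882.
- AUC, piecewise: 0.963 to 0.751.
- Linear model, both contrasts: 0.976 to 0.816.

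**3. What it leaves.** Suppose a covariate has level effect L and adds β at 6 months, growing linearly (effect L + βt per covariate SD), with imbalance d. The fitted constant coefficient is the five-visit average, L + β. The unexplained arm difference is then βd(t − 1): a true slope part βd and a spurious baseline shift of −βd. The error left at 6 months is βd × (1 − pass-through):
- Linear model: βd × 2.5/(7.5 − 25k), or 0.75βd at ρ = 0.5.
- Piecewise model: βd × ρ, or 0.50βd at ρ = 0.5.

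*Scenario A (assumed): L = 0, β = 0.3, d = 0.2.* Unadjusted error: 0.060. At ρ = 0.5, 0.045 and 0.030 remain. The omitted slope term also shifts the fitted correlation. It adds 0.09 × 2.5/5 = 0.045 to the average variance and −0.225/20 = −0.01125 to the average covariance, so ρ becomes 0.48875/1.045 = 0.468. With that value **0.044** (linear) and **0.028** (piecewise) remain. With covariate-by-time terms the remainder is 0.000.

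*Scenario B (assumed): L = 0.4, β = 0.1, d = 0.2.* At ρ = 0.5 the unadjusted errors are 0.08 × 0.25 + 0.02 = 0.04 (linear) and 0.08 × 0.50 + 0.02 = 0.06 (piecewise). After main-effect adjustment the correlation is about (0.5 − 0.16)/0.84 = 0.405, and **0.014** and **0.008** remain.

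*Range.* At ρ = 0.5, with β from 0.1 to 0.3 and d from 0.1 to 0.2, the remainder runs from 0.0075 to 0.045 (linear) and from 0.005 to 0.030 (piecewise). If the effect in Scenario A plateaus at 6 months, 0.023 and 0.039 remain.

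**4. Scale.** With 125 per arm the SEs are √(2 × 0.15/125) = 0.049 (linear) and √(2 × 0.75/125) = 0.1095 (piecewise). Scenario A leaves 0.044/0.049 = 0.90 SE and 0.028/0.1095 = 0.26 SE. Chance imbalance has SD √(2/125) = 0.1265, so 0.2 is 1.6 of its SDs. Over repeated randomizations the linear model's actual SE in Scenario A is √(0.049² + (0.22 × 0.1265)²) = 0.056, where 0.22 = 0.044/0.2. It is 0.049 with covariate-by-time terms.

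**The case against.** A reader might go further and infer that level-shift covariates cancel out of any change-from-baseline contrast, so that the adjustment adds nothing. The documents do not support that. Exact cancellation needs separate arm intercepts and complete data. The analysis section lists no treatment main effect, the power section specifies a common intercept, and the figures above reproduce only with one. The plan also allows up to 25 dropouts per arm by 6 months and fits all available data by maximum likelihood. In an illustrative simulation where dropout depended on the covariate differently by arm, the unadjusted piecewise estimate was off by about 0.05 SD. Main-effect adjustment removed that error under either intercept. The plan's statement that covariates can adjust and absorb variance is therefore fair as far as it goes.

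The defence of leaving the model alone has weight too. Randomization keeps the contrast unbiased in expectation. Stratification by dementia limits imbalance in cognition. The slope effect and imbalance used here are assumed. In the piecewise model the remainder is about 0.03 SD or less in most of the cases shown, against a detectable 0.36 SD.

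This limits the size of the point but does not remove it. The default is the linear model, where the SE is smaller and, when the covariate effect grows linearly, a larger share of the error remains. In addition, the common intercept is stated only in the power section. An analyst coding a separate trajectory for each arm could fit separate intercepts, and with complete data the covariates would then have no effect on the contrasts.

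**Conclusion.** The point holds as a limitation of the adjustment. Under the plan's common-intercept model, the covariates deal with level differences and improve precision. They only partly adjust for imbalance in predictors of rate of change, so describing the contrasts as controlled for every covariate overstates what the model does.

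On the stated assumptions the remaining 6-month error is about 0.044 of 0.060 SD (linear) and about 0.03 (piecewise) for a strong slope effect. It is about 0.014 and 0.008 SD for a weak one. These are errors conditional on an imbalance, not expected bias. They rest on assumed covariate effects, an assumed imbalance, the plan's ρ of 0.5 and complete data. The model structure can be read directly from the plan; the size cannot.

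**What to change.** In the Aim 1 Statistical Analysis section:

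1. Add a covariate-by-time term for each of the five pre-specified covariates. Use covariate-by-visit terms if the piecewise model is fitted.
2. State that the two arms share one baseline mean, as the power section already assumes.

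Keep the covariates and contrasts as they are.

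**Cost.** This is a wording change with no new data. It adds one parameter per covariate in the linear model (five in all) or four per covariate in the piecewise model (20 in all). If the covariates do not predict change, the SE rises by less than 1% on average. For one covariate 0.2 SD out of balance, its correlation with arm is about 0.1, so the factor is at most 1/√(1 − 0.1²) = 1.005. If they do predict change as in Scenario A, the linear model's actual SE falls from 0.056 to 0.049.
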